The brief intervention will screen for food insecurity by a dietitian asking 2 questions to the dietitian service user. A pre-developed 2 item validated screening tool that assesses for food insecurity will be used. It uses the first two questions from the 18 item U.S. Household Food Security Survey. The two-item screen was validated by Hager et al. (2010) who reported a sensitivity of 97% and specificity 83% for identifying an affirmative response for either question. The tool has been validated in U.S as a shorter more practical tool in clinical practice. This is what The American Academy of Paediatrics (2015) endorse.

Once the dietitian has asked the two questions they will use the screening flow chart to advise why food security is important for good health and the clinical outcomes of their dietetic treatment, and then recommend what can be done to help act on food insecurity if present. To do this the dietitian will use two resources as appropriate (BDA Food Fact Sheet, Eat Well Spend Less and resource list for local food aid support). If trained, a referral voucher to a local foodbank will also be completed if appropriate. The dietitian will record the actions they take on the data collection tool.

There may be cases where a dietetic service user is recruited to participate in the study, but the dietitian does not complete the intervention (the 2 screening questions). It is important that the dietetic service user is advised how to access these food aid support resources if the intervention is not completed as their expectations may be raised that they are going to receive this information and they are not fulfilled. The dietetic service user will be advised on the participant information sheet '*Should the dietitian at your appointment not ask you the questions about food insecurity but you would like resources about this, please ask the researcher in the waiting area or contact the lead researcher (contact details on page 3) for this information*'.

STEP 1 ASK: 'I am going to read you two statements that people have made about their food situation. For each statement, please tell me whether the statement was often true, sometimes true or never true for your household in the last 12 months.'

1. "We worried whether our food would run out before we got money to buy more." Was that often true, sometimes true, or never true for your household in the last 12 months?

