2. "The food that we bought just did not last and we did not have money to get more." Was that often true, sometimes true, or never true for your household in the last 12 months?

A response of 'often true' or 'sometimes true' to either question is an indication of food insecurity.

A response of 'never true' to both questions is an indication that food insecurity is NOT present. Steps 2 and 3 advise and act are not required.

STEP 2 ADVISE: Once the dietitian has asked the two questions and a response of 'often true' or 'sometimes true' to either question has been provided, that is an indication of food insecurity. The dietetic service user will then be advised why addressing food insecurity is important for good health and the clinical outcomes of their dietetic treatment.

STEP 3 ACT: The dietetic service user will then be recommended to access a local food support service to address their food insecure status and follow recommendations provided by the British Dietetic Associations - Eat Well Spend Less diet sheet. Literature will be provided for both aspects and will be verbally discussed. For those who cannot read they will be directed to call or access Coventry Foodbank where a volunteer will be able to discuss all the written information with them in more depth. If trained, a referral voucher to a local foodbank will also be completed if appropriate.

Training of the dietitian

The dietitian will receive specific training prior to commencing the study as per the training protocol. The principal method of delivery will be a video tutorial, designed specifically for the study, which will be available to dietitians before and during the study. The video tutorial will be a filmed consultation which will assimilate the necessary skills and confidence required of the dietitian to successfully implement the intervention. The video tutorial will address the lack of knowledge and hence confidence to intervene on food insecurity. There will also be a suggested script to follow. Also included in the training protocol is useful information about food insecurity. If there is any uncertainty about the brief intervention delivery, then the dietitian will be able to contact the lead researcher for clarification.

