- The dietitian deems it inappropriate to make an opportunistic brief intervention on food insecurity. This includes personal and medical reasons known to the dietitian or reasons related to the consultation (for example the dietitian service user has become distressed and it would seem insensitive to complete the intervention at that time).
- Is <18 years of age and their main care giver is <18 years of age
- No interpreter present, therefore the potential participant is unable to understand and speak English sufficiently to give informed consent
- Lacks capacity to give informed consent.
- Has a diagnosed severe eating disorder

Sampling strategy

Dietetic service user: purposive sampling, all dietitian service users attending dietitian clinic where the dietitian is trained to deliver the brief intervention will be invited to participate in the research

Dietitian: purposive sampling, dietitians who undertake dietitian clinics will be invited to participate in the research

Sample size

A sample size has not been predicted as it is a feasibility study. The study needs enough time to test the process and ensure that food insecure individuals are attending clinic where the research is being tested.

It is anticipated to recruit 5 dietitians and attend 10 of their clinics. Each clinic on average has 5 people in it and a 20% DNA rate. This exposes potentially 200 potential recruits to the study.

Outcome measures

1. Feasibility is to be measured by the number of dietetic service users consenting to take part, the number of completed brief interventions and the number of dietetic service users identified with food insecurity.
2. Dietetic service user's acceptability will be measured by the percentage of those identified as food insecure acting on the advice provided. This will be assessed by a telephone call from the researcher to the dietetic service user 2 weeks post intervention. The dietetic service user will also be asked about their experience of the brief intervention during this call. The telephone call will take the nature of a semi structured interview and be audio recorded. Once the telephone call is completed this will be the end of the study for the patient. 2 weeks was selected as there is no current literature to suggest a different timeframe. Self-reporting is acknowledged as a weak design however it is the most feasible and practical way of obtaining the relevant information.

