Recruitment of the dietitian will take place at the dietitian main department. A member of the research team will be invited to attend a department meeting to recruit. The potential participants will be introduced to the research using the participation information sheet and a verbal explanation given by the researcher. The dietitian will be provided with adequate time (with up to 24 hours) to consider their participation in the study. They will have time to read the participant information sheet and will be given an opportunity to ask any questions they may have in order to decide whether they wish to participate in the study or not. If the dietitian is willing to participate in the study, they will keep the participant information sheet and sign the consent form. They will also be provided with information on how to access the necessary training to complete the brief intervention for food insecurity.

5. Withdrawal

The participant can withdraw at any time from the study without giving a reason(s) and without their medical care or rights being affected. Data collected up to the point of withdrawal can only be used after withdrawal if the participant has consented to this.

As the dietetic service user will be asked two questions which may be considered sensitive, if the patient becomes distressed during the study they will be able to withdraw at any time, without giving a reason(s).

6. Duration

It is anticipated that the study period to gather all the necessary data will be 6 months. Study commencement July 2019. Recruitment of the dietitian to take place in July 2019. Data collection in Coventry clinics July 2019 – February 2020.

7. Analysis

Quantitative data analysis

Quantitative results will be reported using descriptive statistics, they will present the percentage of individual's eligible to take part, percentage consenting, percentage screened by the dietitian, percentage food insecure and percentage acting on advice. This data will be analysed using the statistical software package, IBM SPSS Statistics for Windows, Version 25.0 (2017).

Qualitative data analysis

A semi structured interview will be completed with the dietitian service user via telephone and a face to face focus group will be completed with the dietitians to assess the feasibility and acceptability of the implementation of the brief intervention in clinical practice, exploring the opportunities and barriers.

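### Outcome 2 scores people with no current need, and people who have not acted yet, the same as people who rejected the advice, so the percentage does not isolate service-user acceptability

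*Combined protocol and SAP*

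**What the plan says.** Section 3, Intervention, Step 1 puts two statements to the service user. Each asks about the whole preceding year: "Was that often true, sometimes true, or never true for your household in the last 12 months". The rule for a positive screen is: "A response of 'often true' or 'sometimes true' to either question is an indication of food insecurity". Neither question asks about the household's position on the day.

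Step 3 gives everyone who screens positive two pieces of advice. The first is: "The dietetic service user will then be recommended to access a local food support service to address their food insecure status". The second is to "follow recommendations provided by the British Dietetic Associations - Eat Well Spend Less diet sheet".

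Section 3, Outcome measures, item 2 defines service-user acceptability as the "percentage of those identified as food insecure acting on the advice provided". It is assessed by self-report in one telephone call 2 weeks after the intervention, and that call ends the person's participation. On the interval the plan says: "2 weeks was selected as there is no current literature to suggest a different timeframe". The same call is a recorded semi-structured interview about the person's experience.

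Section 7, Quantitative data analysis lists five descriptive percentages. The last two are "percentage food insecure and percentage acting on advice". No breakdown by current need or by reason for not acting is planned, and acting on the advice is not defined further.

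**The concern.** The denominator and the numerator refer to different periods. A household that was short of money ten months ago but is not short now answers truthfully that the statement was sometimes true. It enters the denominator, is pointed to food support, and has little reason to use it in the next fortnight. If it does nothing, it lowers the acceptability percentage exactly as a household that disliked the intervention would. So does a household that is in need and intends to act but has not yet done so.

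Acceptability is part of the first research aim, and item 2 is the only number assigned to it for service users. A low result could mean rejection, need that has passed, or too little time. The planned table could not tell these apart.

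**Working it through.** **The plan's own figure.** Section 3, Sample size gives 5 dietitians, 10 clinics each, 5 people per clinic and 20% non-attendance: 5 × 10 × 5 × (1 − 0.20) = 200 potential recruits. The stated 200 is reproduced.

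**Scale of the denominator.** Section 1 cites prevalences of 10.1% and 13%. With full consent and full screening, 200 × 0.101 = 20.2 and 200 × 0.13 = 26, so about 20 to 26 people if the share screening positive equals the cited prevalence. Two things could raise this. Section 3 aims for clinics in deprived areas. The quoted sensitivity (97%) and specificity (83%), if they applied here, would also give more screen-positives: 0.97 × 20.2 + 0.17 × 179.8 = 50.2, and 0.97 × 26 + 0.17 × 174 = 54.8. Incomplete consent or screening would lower it. On any of these counts, a handful of people moves the percentage visibly.

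**Effect on the percentage.** Let *a* be the share acting among positives with current need, *s* the share of positives without current need, and *b* the share of the latter who act.

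Reported percentage = a(1 − s) + b·s

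Difference from uptake among those in need = −s(a − b)

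The difference is negative when b < a, zero when b = a, and positive when b > a. The documents give none of the three values, so all are assumed.

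| a (assumed) | s (assumed) | b = 0 | b = a/2 | b = a |
|---|---|---|---|---|
| 60% | 20% | 0.60 × 0.8 = 48% | 48% + 0.30 × 0.2 = 54% | 60% |
| 60% | 50% | 0.60 × 0.5 = 30% | 30% + 0.30 × 0.5 = 45% | 60% |
| 40% | 20% | 32% | 36% | 40% |
| 40% | 50% | 20% | 30% | 40% |
| 80% | 20% | 64% | 72% | 80% |
| 80% | 50% | 40% | 60% | 80% |

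**In whole people (assumed counts).** Take 20 positives, of whom 5 have no current need and do not act, while 9 of the other 15 act. The planned figure is 9/20 = 45%; among those with need it is 9/15 = 60%.

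**Delay.** People in need who have not acted by 2 weeks lower *a* itself. Restricting the denominator to current need does not correct this; only the recorded reason would show it.

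**The case against.** The strongest objection is that a passed shortage does not by itself make someone a non-actor. The advice has two parts, and a household no longer short of food can still follow the budgeting sheet. The Intervention section also has the dietitian use the resources, and complete any voucher, as appropriate to the person. A reader might infer that everyone whose shortage has passed is counted as not accepting the intervention. The documents do not support that: such a person counts against acceptability only by not acting, and whether following one part of the advice is enough is left undefined. This objection stands. It limits the size of the effect but removes it only if people without need act as often as people in need.

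A reader might also infer that the result must be too unfavourable. That does not follow either. This mechanism pulls downward when b < a, but the answer is self-reported to the researcher, which the plan acknowledges as weak and which could inflate it. The net direction is not known.

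The interview is a partial safeguard. Sections 2 and 7 have it explore barriers, and framework analysis with emergent coding could bring out that help was no longer needed. This is a fair point for a mixed-methods study, but nothing carries such reasons into the percentage.

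Finally, the study is descriptive, and no visible success threshold hangs on this figure. The flow chart and data collection tool are not in the available text, so an item on current need there cannot be excluded.

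**Conclusion.** The point holds in a limited form. As written, outcome 2 mixes the timing of need and the timing of action with acceptance of the advice. It is lower than acceptance among people in need whenever people without current need act less often.

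The size is unknown. With an assumed 60% uptake among those in need and an assumed 20% to 50% of positives without current need, the reported figure is 48% to 30% at zero uptake in the latter group, 54% to 45% at half the rate, and 60% at the same rate. The lower pair is the worst case, not an expected result.

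The documents do not show that the 12-month screen or the 2-week call is wrong in itself. The gap is that nothing quantitative links the two. The change is worth making because it is cheap and leaves the planned figure intact.

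**What to change.** Keep the screening tool and the 2-week call, and add three fixed items to the call:

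1. Before any question about action, ask whether the household was short of food, or of money for food, at the time of the appointment or since.
2. Record action separately for each part of the advice: use of a food support service, and following the Eat Well Spend Less sheet. State in item 2 which of these counts as acting.
3. For those who did not act, code the main reason: no current need; not yet; tried and could not; did not want to.

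In section 7, report the percentage acting among all screen-positives as planned. Beside it, report the percentage among those with current need, with numerators and denominators, and show the distribution of reasons. Do not add a rule that only unwillingness counts against acceptability. Such a rule would excuse most non-action and push the figure upward; with the reasons shown, readers can judge for themselves.

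The cost is a few questions in a call already planned and some extra table rows. The second percentage has a smaller denominator, drawn from only about 20 to 26 positives if the share screening positive matches the cited prevalence and all 200 take part. Need would be one more retrospective self-report, open to after-the-fact justification by people who did not act. Asking it first reduces that risk but does not remove it.

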3. Dietitian's acceptability of the intervention will be analysed quantitatively by the number of records of consented dietitian service users not screened. At the end of the study Dietitians will be invited to attend a focus group with other dietitians who completed the brief intervention for food insecurity to discuss the feasibility and acceptability of the brief intervention. Once the focus group has been completed this will be the end of the study for the Dietitian. A focus group is more time-efficient than completing one to one interviews and allows thoughts to be developed and shaped by peer-to-peer discussion, rather than a collection of single reflections

4. Consent and recruitment of participants

Dietitian service user

All dietitian services users attending dietitian clinics where the brief intervention is being tested will be invited to participate in the research. Recruitment of the dietitian service user will take place in the dietitian waiting area whilst they are waiting for their appointment. The potential participants will first be approached by the researcher in which a verbal explanation and a copy of the participant information sheet will be given. The dietetic service user will be provided with adequate time to consider their participation in the study. They will have time to read the participant information sheet and will have the opportunity to ask any questions they may have, in order to decide whether they wish to participate in the study or not. If the dietitian service user is willing to participate in the study, they will keep the participant information sheet and sign the consent form.

Dietitian

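### Outcome 3 reads consented-but-unscreened service users as a measure of dietitian acceptability without separating who stopped the screening, so some service-user refusals and departures would count against the dietitian.

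*Combined protocol and SAP*

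**What the plan says.** Section 3, Outcome measures, item 3 gives the only quantitative measure of the dietitian's view of the intervention: "acceptability of the intervention will be analysed quantitatively by the number of records of consented dietitian service users not screened". It states no denominator, no breakdown by reason and no exclusions. The same item adds an end-of-study focus group with dietitians who delivered the intervention.

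Section 4 places consent before the consultation: "Recruitment of the dietitian service user will take place in the dietitian waiting area whilst they are waiting for their appointment". Section 5 lets any participant withdraw at any time without a reason. It ties this to the intervention itself, noting that the two questions may be sensitive and that a service user may become distressed. It also limits what can be used afterwards: "Data collected up to the point of withdrawal can only be used after withdrawal if the participant has consented to this".

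Section 3, Intervention, expects some consented people to go unscreened, but describes this only from the dietitian's side: "There may be cases where a dietetic service user is recruited to participate in the study, but the dietitian does not complete the intervention". On recording, it says: "The dietitian will record the actions they take on the data collection tool". The tool itself is not reproduced.

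The exclusion criteria in section 3 include the case where "The dietitian deems it inappropriate to make an opportunistic brief intervention on food insecurity", with distress during the consultation as an example. Section 7 lists the percentage screened among the descriptive results and does not split the remainder by reason.

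**The concern.** There is an interval between signing consent and being asked the two questions. In that interval, and at the moment of asking, the service user can end the process. The dietitian may have been willing to ask, or may actually have asked. The resulting record is still consented and not screened, which is all that outcome 3 looks at.

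Refusal after consent is evidence about the service user's acceptance of the intervention. No stated service-user measure captures it:

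- Outcome 2 is a percentage of those identified as food insecure, so a person who was never screened cannot enter it.
- The telephone interview is timed from the intervention, so as written it does not reach people who did not receive one.

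The study aims to describe barriers from both perspectives. Dietitians not asking and service users not answering are different barriers with different remedies, and the count as defined merges them under the dietitian's name.

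**Working it through.** **The plan's own figure.** Section 3, Sample size, gives 5 dietitians, 10 clinics each, 5 people per clinic and 20% non-attendance: 5 × 10 × 5 × (1 − 0.20) = 200 potential recruits. This reproduces and is not in dispute. Non-attenders are removed before consent, so they do not feed outcome 3.

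**Which cases enter the count as written.**

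| Consented service user who… | Enters outcome 3? | Reflects the dietitian? |
|---|---|---|
| is seen, and the dietitian does not ask | Yes | Yes, apart from permitted exclusions |
| is seen, and the dietitian judges the intervention inappropriate | Not stated | Not necessarily: it is an exclusion criterion |
| is asked and declines | Yes, on the natural reading | No |
| leaves before being seen | Yes | No |
| formally withdraws before screening | Only if they agreed to use of their data | No |

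**Size.** The documents give no consent, refusal, departure or withdrawal rates, so everything from here rests on assumption. Let *d* be the proportion of consented people not screened because of the dietitian. Let *s* be the proportion not screened because of the service user and whose records remain usable. With *n* consented:

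- outcome 3 = *n*(*d* + *s*)
- share not due to the dietitian = *s* / (*d* + *s*)
- count relative to the dietitian-driven number = 1 + *s*/*d*

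The consent rate cancels from the last two. Assumed ranges: *d* 5% to 20%, *s* 2% to 10%.

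| *d* | *s* | Share not due to the dietitian | Count ÷ dietitian-driven number |
|---|---|---|---|
| 20% | 2% | 2/22 = 9% | 1.1 |
| 10% | 5% | 5/15 = 33% | 1.5 |
| 5% | 10% | 10/15 = 67% | 3.0 |

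**In numbers of people.** Assume 50% of the 200 consent (100), with *d* = 10% and *s* = 5%. Outcome 3 then reads 10 + 5 = 15, or 15% of those consented, and 5 of the 15 (33%) do not reflect the dietitian. Restricted to people seen but not asked, the numerator is 10. The denominator of those consented and seen lies between 95 (all five left unseen) and 100 (all five declined when asked). The result is 10/95 = 10.5% to 10/100 = 10.0%.

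**The case against.** The strongest reply has four parts.

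**Withdrawal.** A reader might infer that every service user who withdraws is scored against the dietitian. The documents do not support that. Section 5 bars use of a withdrawn person's data unless they agreed to it, so some withdrawals would drop out of the count. This narrows the point but does not remove it: refusal or departure without formal withdrawal is untouched by that rule.

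**Meaning of not screened.** The term is undefined for someone who is asked and declines. The protocol usually describes non-completion as the dietitian's act, so outcome 3 could be read as meaning only that the dietitian did not ask. That intent is plausible, but the outcome does not say so. Even on that reading, a person who left before being seen was not asked and would still be counted.

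**Other information.** The data collection tool is not reproduced and may already hold a reason field. The focus group lets dietitians say that service users refused. Both are fair. However, outcome 3 as defined would not use a reason field, and a group discussion cannot reclassify records. A reader might infer that the study will wrongly conclude that dietitians avoid the questions. The focus group makes that less likely, and the documents do not establish it.

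**Consequences.** The study is descriptive, with no hypothesis test and no progression threshold attached to this count. That limits the harm to interpretation. It does not make the number a sound measure of dietitian acceptability.

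**Conclusion.** The point stands in a limited form. Outcome 3, followed as written, attributes to the dietitian some non-screening that the service user caused: departures before being seen and, on the natural reading, refusals when asked. Formal withdrawals are affected only where the person agreed to use of their data. No other outcome or analysis corrects the number.

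The size is unknown. The range of about 9% to 67% follows entirely from the assumed 5-20% and 2-10%. It shows that the effect could be minor or could dominate the count. The threefold figure at the top of the range should not be read as an estimate, because it arises only when service-user stopping is assumed to be twice as common as dietitian non-screening.

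**What to change.** 1. **Redefine outcome 3** as the number of consented service users still in the study and seen by the dietitian but not asked the two questions. Report it over the number consented and seen.
2. **Record who stopped the screening** on the data collection tool, if it does not already do so: *dietitian did not ask* / *service user declined or withdrew* / *not seen*. No reason is requested from the service user, so the right in section 5 is respected.
3. **Within *did not ask*, show on a separate line** the cases the dietitian deemed inappropriate under the exclusion criterion. Otherwise the category would still mix unwillingness with a permitted exclusion.
4. **Report the number of service users who declined** as a separate descriptive line beside outcome 2. It cannot go inside that outcome's percentage, because the food-security status of decliners is unknown.
5. **Include withdrawn participants** in any of these tallies only as section 5 permits, and say so.

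The cost is one item on an existing form and a few sentences in the outcome and analysis sections. The small downside is that the dietitian classifies the case. For people who leave or withdraw before the appointment, the researcher in the waiting area can confirm the entry.
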